1.2 Clinical Investigation Objectives

The primary objective is to confirm the safety and performance of the next generation MitraClip® NTR and MitraClip® XTR Systems within a contemporary real-world setting.

1.3 Clinical Investigation Design

This is a Prospective, Multi-Center, Single-Arm, International, Post Market, Observational Study designed to collect real-world data on the use of the next generation MitraClip NTR and MitraClip XTR Systems. Up to 1,000 commercial subjects from the EU or US will be included in the analysis for the MitraClip EXPAND Study. Follow-up echocardiograms will be collected at 30 days and 12 months post-procedure visits with an additional clinical follow-up visit or phone call at 6 months.

The study will group subjects into cohorts for analysis based upon select pre-defined mitral valve anatomic criteria. This approach is supported by recent literature that shows an evolution of the use of MitraClip in which a significant percentage of cases presented in post-market studies differ in patient selection from the cases included in early clinical studies (i.e. EVEREST, EVEREST II). The analysis of these cohorts will allow for the evaluation of outcomes and identification of trends in patient selection and outcomes in contemporary real-world use in the context of historical MitraClip data.

1.4 Endpoints

1.4.1 Safety and Performance Measures

• Safety

The assessment of safety will include all occurrences through 30 days post procedure.

Occurrence of Major Adverse Events (MAE) at 30 days

MAE is defined as a composite of all-cause Death, Myocardial Infarction, Stroke, or non-elective Cardiovascular (CV) surgery for device related complications (CEC adjudicated).

Performance

The assessment of performance measures will include all data reported at 30-day visits for this study. MR Reduction to \leq 2+ at 30 days

1.4.2 Acute Measures

• Acute Procedural Success (APS) defined as successful implantation of the MitraClip® device with resulting MR severity of 2+ or less on discharge Echocardiogram (30-day echocardiogram will be used if

discharge is unavailable or uninterpretable). Subjects who die or undergo mitral valve surgery before discharge are considered to be an APS failure

- Acute Device Success defined as successful implant of the MitraClip device without the occurrence of a Device-Related Complication (including mitral valve stenosis, device embolization, Single Leaflet Device Attachment (SLDA), latrogenic atrial septal defect, or myocardial perforation) through discharge.
- Use of MitraClip NTR or MitraClip XTR: to include the percentage of cases with each device and an assessment of reason for device selection
- Procedure Time: defined as the time elapsed from the first intravascular catheter placement or transesophageal echocardiogram (TEE) to the removal of the last catheter and TEE
- Number of Clips Implanted
- Number of Attempted Grasps defined as the number of attempts to stabilize leaflets by the open Clip
- User feedback
- Device-Related Complications defined as the occurrence of one the following adverse events that is
 determined by investigator assessment to be probably, possibly or definitely related to the MitraClip
 device.
 - Mitral valve stenosis
 - SLDA
 - Device Embolization
 - Iatrogenic atrial septal defect
 - Myocardial perforation
 - Need for mitral valve replacement instead of repair due at least in part to the MitraClip procedure or the presence of the MitraClip device
- In-hospital MAE defined as the number of MAEs that occur prior to discharge from hospitalization in which MitraClip Procedure was performed
- MR Reduction to ≤1+ at 30 days

1.4.3 Clinical Measures (Discharge, 30-day, 6-month and 12-month):

- All-cause Mortality
- Heart Failure Hospitalization
- MAE
- Device-Related Complications

1.4.4 Functional Improvement Measures (Baseline, Discharge and 12-month)

- New York Heart Association (NYHA) functional class improvement
- Quality of Life (QOL) assessed using the Kansas City Cardiomyopathy Questionnaire (KCCQ)

1.4.5 Site Reported Echocardiographic Measures (Baseline, Post Procedure, 30-day and 12-month)

- MR Severity Grade
- Effective Regurgitant Orifice Area (EROA) as measured by measured by PISA method
- Coaptation Measures (depth/length)
- Flail Measures (gap/width)
- Grasping Area Anatomy (measure cleft or scallop if significant)
- Assess chordal support
- Regurgitant Jet(s) Position and Quantity
- TR Severity: None, Mild, Moderate or Severe

1.4.6 Echocardiographic Measures from echo core lab (Baseline, Post Procedure, 30-day and 12- month)

- MR Severity Grade
- Effective Regurgitant Orifice Area (EROA) as measured by measured by PISA method
- Coaptation Measures (depth/length)
- Flail Measures (gap/width)
- Grasping Area Anatomy (measure cleft or scallop if significant)
- Assess chordal support
- Regurgitant Jet(s) Position and Quantity
- TR Severity: None, Mild, Moderate or Severe

2.0 ANALYSIS CONSIDERATIONS

2.1 Analysis Populations

2.1.1 Analysis Population

2.2 Statistical Methods

2.2.1 **Descriptive Analyses**

Descriptive analysis will be performed to summarize baseline characteristics, acute measures, functional improvement, echocardiographic, clinical measurements, safety and performance measurements. Depending on the type of data (e.g., continuous or categorical), statistical methods described in the following sections will be used.

2.2.1.1 Descriptive Statistics for Continuous Variables

For continuous variables (e.g., age, etc.), results will be summarized as number of observations, means, and standard deviations, and where applicable, with quartiles, minimums, maximums, and 95% confidence intervals for the means. Differences between two groups, where specified, will be summarized with differences of the two means, and 95% confidence intervals for the difference between the means.

A two-sample t-test or Wilcoxon rank sum test, depends on the normality of the data, will be used to test the difference between subgroups. A paired t-test or Wilcoxon sign test will be used to test the difference of measurements between baseline and follow-ups.

2.2.1.2 Descriptive Statistics for Categorical Variables

For binary variables (e.g. gender, APS, etc.), results will be summarized with subject counts and percentages/rates, and where applicable, with exact 95% Clopper-Pearson¹ confidence intervals. Differences between the two groups, when specified, will be summarized with the difference in percent and the Newcombe² score 95% confidence interval for the difference of two percentages.

For endpoints of interest, relative risks (i.e., the ratio of rates), confidence interval for the relative risks, the difference in rates and the confidence interval for difference in rates, and p-values may also be presented for hypothesis generating purposes.

2.2.2 Survival Analyses

Survival analysis will be conducted to analyze time-to-event variables. Subjects without events will be censored at their last known event-free time point. Subjects who withdrew from the study will be censored at the date of withdrawal. Survival curves will be constructed using Kaplan-Meier⁴ estimates. Summary tables for events of interest will include event (failure) rates, Greenwood standard error and confidence interval for the event rates.

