9.4 Statistical Analyses

9.4.1 Endpoint Analysis

The intent of this study is to collect contemporary data in a real-world setting. All endpoints for this study will support a post-market assessment of device safety and performance. Descriptive analysis will be performed on the study data. Depending on the type of data (e.g., continuous or categorical), statistical methods described in this section below will be used.

For continuous variables, such as age, means, standard deviations, and 95% confidence intervals for the mean will be calculated.

For binary variables such as APS, counts, percentages, and 95% confidence intervals based on Exact Clopper-Pearson method will be calculated.

For time to event data such as all-cause mortality, Kaplan-Meier analyses will be performed.

For recurrent event data such as recurrent heart failure hospitalizations at pre- and post-procedure, data will be analyzed using a generalized linear model, such as Poisson regression model.

Results from this study will be presented within the context of the literature on the MitraClip.

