Degenerative MR etiology was present in a majority (85.9%) of patients, whereas functional MR was noted in 17.5% (FMR only 8.6%; mixed etiology 8.9%). Ninety-three percent (93%) of patients presented with 3+ or 4+ MR at baseline. Significant left ventricular dilation (end-systolic dimension ≥ 40 mm) was present in 32.2%. The median LVEF was 55% and 35.4% of the patients had an LVEF $< 50\%$. Baseline mean mitral gradient was ≥ 5 mm Hg in 9.2%, and the MV area was < 4 cm² in 20.5%. Severe tricuspid regurgitation was present in 16.0% of the patients.

The MitraClip was predominantly implanted in the A2-P2 region (82.8% of cases). MR reduction to $\leq 2+$ was achieved in 93.0% of patients, while MR grade $\leq 1+$ was achieved in 61.8%. Single-leaflet device attachment occurred in 1.5% of treated patients. There were 4 reported cases of device embolization (0.1%). Major or life-threatening bleeding (VARC-2 criteria) occurred in 3.9%. The rates of stroke (0.4%) and myocardial infarction (0.1%) were both low. Twenty patients (0.7%) had in-hospital conversion to open cardiac surgery. Overall in-hospital mortality was 2.7%. The median length of hospital stay was 2 days and a majority (85.9%) of the treated patients were discharged directly home.

A total of 1,867 patients (63.2%) from 139 hospitals had records that could be linked to CMS administrative claims. Patients with linked CMS claims data tended to be older, had a lower rate of comorbidities such as diabetes and prior myocardial infarction, and were less likely to have functional MR. However; the STS-predicted risks of operative mortality for MV repair and MV replacement were higher in patients with linked CMS claims data compared to those without linked CMS claims data.

In this cohort, 30-day mortality, including in-hospital events, was 5.2% and the rate of re-hospitalization for heart failure was 4.9%. A majority (95.5%) of patients were discharged from hospital with MR $\leq 2+$, alive and free from MV surgery at 30 days.

One-year mortality in patients with linked CMS claims data was 25.8% and the rate of re-hospitalization for heart failure at 1 year was 20.2%. The combined endpoint of death or heart failure re-hospitalizations at 1 year occurred in 37.9% of the patients. These endpoints were lower for patients who had degenerative MR etiology (24.7%, 20.5%, and 35.7%, respectively) compared to those who had functional MR etiology (31.2%, 32.6%, and 49.0%, respectively).

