The subgroup of patients with severe tricuspid regurgitation also had significantly worse outcomes, with 1-year cumulative incidences of 38.5%, 31.5%, and 54.3% for death, heart failure re-hospitalization, and the combined endpoint of death and heart failure re-hospitalization, respectively.

Similarly, a graded effect was noted when comparing cumulative incidence of death and the combined endpoint of death or heart failure re-hospitalization at 1 year by discharge MR. As expected, better outcomes were observed in patients discharged with MR $\leq 1+$ (21.7% and 35.7%, respectively) compared to those discharged with MR 2+ (29.2% and 39.2%, respectively), and MR $\geq 3+$ (48.9% and 54.4%, respectively).

At 1 year, 6.2% of patients with linked CMS claims data required a second MitraClip procedure. The cumulative rate of stroke was 2.7%.

Variables associated with mortality or re-hospitalization for heart failure after multivariate adjustment were increasing age, lower baseline LVEF, worse post-procedural mitral regurgitation, moderate or severe lung disease, dialysis, and severe tricuspid regurgitation.

Based on these data, the authors conclude that the MitraClip procedure is being performed effectively and safely for severely symptomatic patients with MR and prohibitive surgical risk in the United States and contend that the observed mortality and re-hospitalizations for heart failure are related to age and associated with decreased LVEF, functional MR, severe tricuspid regurgitation, moderate or severe lung disease, and post-procedural residual MR.

Non-EVEREST Criteria

Patients treated with the MitraClip device as part of the EVEREST program had to meet specific anatomic inclusion criteria. These criteria, included a regurgitant jet origin associated with the A2 to P2 segments of the mitral valve and, for patients with functional MR, a coaptation length of at least 2 mm, a coaptation depth of no more than 11 mm, and for patients with leaflet flail, a flail gap <10 mm and a flail width <15 mm. In addition, leaflet anatomy which may preclude device implantation, proper MitraClip device positioning on the leaflets or sufficient reduction in MR were excluded. This may include:

Evidence of calcification in the grasping area of the A2 and/or P2 scallops

Presence of a significant cleft of A2 or P2 scallops

More than one anatomic criteria dimensionally near the exclusion limits

Bileaflet flail or severe bileaflet prolapse

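### The SAP has no rule for death before a non-fatal event: if 12-month heart failure hospitalisation is reported by Kaplan-Meier with deaths censored, it would be overstated by about 1 to 3 points overall

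*SAP*

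**What the plan says.** SAP 2.2.2 opens in general terms: "Survival analysis will be conducted to analyze time-to-event variables". Its censoring rule is "Subjects without events will be censored at their last known event-free time point". Subjects who withdraw are censored at withdrawal. Curves are Kaplan-Meier, and the tables give failure rates with Greenwood standard errors. No rule covers death before a non-fatal event, and no competing-risk method is visible.

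SAP 1.4.3 lists "Heart Failure Hospitalization" and device-related complications among the measures to be reported at discharge, 30 days, 6 months and 12 months. SAP 2.3 sends every endpoint of section 1.4 to section 2.2 as a whole, without matching endpoints to methods. Section 2.2 also contains a method for binary variables, under which "results will be summarized with subject counts and percentages/rates".

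Protocol 9.4.1 is a little more specific. Its Kaplan-Meier example is mortality: "For time to event data such as all-cause mortality, Kaplan-Meier analyses will be performed". It treats repeated admissions separately: "For recurrent event data such as recurrent heart failure hospitalizations at pre- and post-procedure, data will be analyzed using a generalized linear model", for example a Poisson model. The visible SAP does not carry that model forward.

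**The concern.** A subject who dies without having been hospitalised for heart failure is, for that outcome, a subject without an event. Read literally, SAP 2.2.2 censors that subject at or before death. Kaplan-Meier then treats the dead as if they could still be admitted later. One minus Kaplan-Meier therefore estimates admission in a hypothetical setting where nobody dies, which is not the proportion of treated patients who are hospitalised.

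Two uses of the result would suffer. Protocol 1.1 and 9.4.1 and SAP 1.3 place the findings in the context of historical MitraClip data. At least one set of benchmark figures, for severe tricuspid regurgitation (TR) in the US registry, is explicitly given as "1-year cumulative incidences of 38.5%, 31.5%, and 54.3% for death, heart failure re-hospitalization, and the combined endpoint". A Kaplan-Meier figure set beside a cumulative incidence would look worse for an unchanged device. The excess also grows with mortality, so contrasts between groups with different death rates would shift.

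**Working it through.** **Nothing to reproduce.** Neither document states an expected 12-month rate of heart failure hospitalisation (HFH) or death for this study. The check therefore uses the historical rates in Protocol Appendix IV.

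**Direction.** The cumulative incidence of HFH adds up the HFH hazard over subjects who are still alive and not yet hospitalised. One minus Kaplan-Meier applies the same hazard to a larger notional group, because deaths do not deplete it. It cannot be lower than the cumulative incidence, and it is higher when deaths come before later admissions.

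**Main calculation.** Take the published HFH figure as a cumulative incidence *c*, and the published death-or-HFH composite as *k*, with constant hazards over one year:

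- total hazard L = −ln(1 − k)
- HFH hazard h = L × c / k
- 1 − KM = 1 − exp(−h)
- excess = (1 − KM) − c

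For the US registry overall: L = −ln(1 − 0.379) = 0.4764; h = 0.4764 × 0.202/0.379 = 0.2539; 1 − KM = 22.4%; excess = 22.4 − 20.2 = 2.2 points.

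| Source (Protocol Appendix IV) | HFH | Composite | 1 − KM | Excess (points) |
|---|---|---|---|---|
| European pilot registry, all | 22.8% | 31.0% (100 − 69.0) | 23.9% | +1.1 |
| US registry, all | 20.2% | 37.9% | 22.4% | +2.2 |
| US registry, degenerative MR | 20.5% | 35.7% | 22.4% | +1.9 |
| US registry, functional MR | 32.6% | 49.0% | 36.1% | +3.5 |
| US registry, severe TR | 31.5% | 54.3% | 36.5% | +5.0 |

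In the US figures the functional-minus-degenerative contrast widens from 32.6 − 20.5 = 12.1 points to 36.1 − 22.4 = 13.7 points.

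**Variants.**

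- *Total mortality as the competing hazard.* Set d = −ln(1 − mortality) and solve h/(h + d) × [1 − exp(−(h + d))] = c for h. US registry overall (mortality 25.8%): 1 − KM = 23.2%, +3.0. European registry (15.3%): +1.9. REALISM high-risk arm (146/628 = 23.2% deaths, 17.8% hospitalised): +2.4. US functional MR gives +5.9 and severe TR +7.5. This variant gives subjects who have not been hospitalised the mortality of the whole cohort, which exceeds the death-first hazard implied by the composite (US overall: 0.4764 − 0.2539 = 0.2225, against d = 0.2984).
- *Published figure already Kaplan-Meier.* If the European 22.8% is itself one minus Kaplan-Meier, the implied cumulative incidence is 21.6% and the gap is 1.2 points.
- *Hazards not constant.* The extreme case puts every death without HFH before any admission: excess = c/(1 − (k − c)) − c. This gives 4.3 points for the US registry overall, 2.0 for the European registry and 9.3 for US severe TR.

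**An oddity in the inputs.** The US overall HFH figure (20.2%) is below both of its etiology figures (20.5% and 32.6%), although overall mortality and the composite each lie between theirs. The result is not sensitive to this. Putting the European 22.8% in place of 20.2%, with the composite held at 37.9%, gives h = 0.4764 × 0.228/0.379 = 0.2866, 1 − KM = 24.9% and an excess of 2.1 points.

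**Scale.** For a rate of 20% with 1,000 subjects, the 95% half-width is 1.96 × √(0.2 × 0.8/1000) = 2.5 points. The whole-cohort excess is of similar order, and unlike sampling error it does not shrink with more subjects.

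**The case against.** The strongest reply is that the plan never says HFH will be analysed by Kaplan-Meier. The protocol's Kaplan-Meier example is all-cause mortality, where nothing competes. Its named model for recurrent HFH is of Poisson type, and SAP 2.2.1.2 offers plain percentages. SAP 2.2 may also be incomplete as published: 2.1.1 and the subgroup list in 2.7 show no content, 2.2.3 begins without an introduction, and reference 3 is not cited in the visible text. All of this stands, and it makes the point conditional.

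It does not remove the point, because neither alternative gives a sound 12-month proportion. Follow-up is unequal by design: subjects with an attempted procedure but no implant are in the analysis population and are followed for 30 days only (Protocol 3.1, 3.2, 7.3.1), and a plain percentage ignores that. The recurrent-event model compares admission rates before and after the procedure; it does not estimate the proportion hospitalised. SAP 2.2.2 is the only visible method that handles incomplete follow-up.

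It can also be said that the comparison with history is contextual, with no test or goal for HFH, and that the benchmarks are mixed. Protocol Appendix IV uses the term cumulative incidence only for the severe-TR and discharge-MR groups of the US registry. It calls the other US HFH figures rates, and the European figure is an estimated rate whose estimator is not given. That stands and limits how firmly a mismatch with the benchmarks can be asserted.

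**Conclusion.** The gap in SAP 2.2.2 is real, and its effect is conditional. If 12-month first HFH is reported as one minus Kaplan-Meier with deaths censored, it would exceed the true cumulative proportion hospitalised by about 1 to 3 points for the whole cohort. In a high-mortality subgroup such as severe TR the excess would be about 5 points. It would be uneven across groups: +1.9 in degenerative and +3.5 in functional MR on US figures.

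A reader might infer something stronger: that HFH will be overstated by 2 to 5 points in this study, and that contrasts by valve anatomy will be distorted too. The documents do not support that. Neither assigns HFH to Kaplan-Meier or says in terms that deaths are censored. The 5-point figure belongs to one US subgroup, and the European registry gives about 1 point while the study enrols in both regions. No figure in the documents allows the effect to be computed for the complex and non-complex anatomy groups or for device-related complications.

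The sizes assume that historical rates transfer to this study, that hazards are constant, and that the US figures are cumulative incidences. Confidence is moderate. MAE contains death, and MR reduction at 30 days is not a time-to-event outcome, so neither 30-day headline measure is affected.

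**What to change.** Amend SAP 2.2.2 as follows:

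- Keep Kaplan-Meier for all-cause death, MAE and any composite that includes death.
- For first HFH and other non-fatal time-to-event outcomes, such as device-related complications, declare death a competing event and report the Aalen-Johansen cumulative incidence.
- Show the death-or-HFH composite beside it, so that a low hospitalisation figure cannot be read without the mortality that accompanies it.
- State in SAP 2.3 which method produces the 12-month HFH figure.
- Carry over the Protocol 9.4.1 generalized linear model for recurrent HFH as a separate analysis.

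Gray's test for subgroup comparisons is optional, since SAP 2.7 describes the subgroup analyses as exploratory. The cost is a few lines of SAP text and a standard SAS routine. No new data are needed, because deaths and their dates are already required for the mortality analysis.

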5.5 Subject Discontinuation

Subjects shall remain in the study until completion of the required follow-up period; however, a subject's participation in any clinical study is voluntary and the subject has the right to withdraw at any time without penalty or loss of benefit. Conceivable reasons for discontinuation may include, but not be limited to, the following:

- Subject death
- Subject voluntary withdrawal
- Subject withdrawal by physician as clinically-indicated
- Subject lost-to follow-up as described below

The Sponsor must be notified of the reason(s) for subject discontinuation. The site will provide this information to the Sponsor. Investigators must also report this to their respective IRB/EC as defined by their institution's procedure(s).

No additional follow-up will be required or data recorded from subjects once withdrawn, except for the status (deceased/alive).

Lost-to-Follow-up:

If the subject misses two consecutive scheduled follow up time points and the attempts at contacting the subject detailed below are unsuccessful, then the subject is considered lost to follow-up. Site personnel shall make all reasonable efforts to locate and communicate with the subject (and document these efforts in the source documents), including the following, at each contact time point:

- A minimum of 2 telephone calls on different days over a 30-day period to contact the subject should be recorded in the source documentation, including date, time and initials of site personnel trying to make contact.
- If these attempts are unsuccessful, a letter (certified if applicable) should be sent to the subject.
- If a subject misses one or more non-consecutive follow-up contact time points it will be considered a missed visit. The subject may then return for subsequent visits. If the subject misses two consecutive time points and the above-mentioned attempts at communicating with the subject are unsuccessful, the subject will be considered lost-to-follow-up.

Note: Telephone contact with General Practitioner, non-study cardiologist or relative without presence of subject or indirect documentation obtained via discharge letters will not be considered as subject contact.

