6.4.1 Follow-Up Imaging

At the 30-day and 12-month follow-up visits a TTE should be conducted per standard of care. TTEs will be collected by the Sponsor for future reference and may be compared to baseline and/or follow-up TTEs.

During the follow-up period for this study (12 months) any unscheduled echocardiograms, either TEE or TTE, should be submitted to the Sponsor.

Table 2 outlines the assessment schedule for this study.

Table 2. Clinical Assessment Schedule

Required Assessments to be Collected	Pre-Treatment	Treatment	DIS	30-D	6-M	1-Y
				-14/+60 days	-30/+90 days	-30/+90 days
Informed Consent	X					
Medical History	X					
Medical Exam and Reporting of Vitals	X		X	X		X
NYHA Classification	X		X	X		X
KCCQ Survey	X			X		X
6 Minute Walk Test (Only if standard of care)	X			X		X
Adverse Events ¹		X	X	X	X	X
Transthoracic Echocardiography (TTE)	X	X ²	X	X		X
Transesophageal Echocardiography (TEE)	X	X ²				
Unscheduled Echocardiogram (TTE or TEE)			X	X	X	X

1. Adverse Events to be collected in this study include: cardiovascular events, device-related complications (as defined in section 4.2), and events classified as MAEs (as defined in section 4.1)
2. TTE and TEE during treatment should be submitted for the study only if capturing TTE and TTE echoes is part of standard of care.

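### For 12-month all-cause mortality, SAP 2.2.2 censors withdrawn subjects at withdrawal and so sets aside deaths and known-alive time that Protocol 5.5 allows to be recorded

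*SAP*

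**What the plan says.** All-cause mortality is a clinical measure at discharge, 30 days, 6 months and 12 months (Protocol 4.3, SAP 1.4.3). Protocol 9.4.1 names the method: "For time to event data such as all-cause mortality, Kaplan-Meier analyses will be performed".

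SAP 2.2.2 has two censoring sentences for time-to-event variables. The first is "Subjects without events will be censored at their last known event-free time point". The second is "Subjects who withdrew from the study will be censored at the date of withdrawal". Neither makes an exception for mortality.

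Protocol 5.5 ends data collection at withdrawal with one exception: "No additional follow-up will be required or data recorded from subjects once withdrawn, except for the status (deceased/alive"). Section 5.9 of the XTR PMCF protocol repeats this. Protocol 5.5 also lists, among the reasons for discontinuation, "Subject withdrawal by physician as clinically-indicated".

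The visible text on endpoint analysis and missing data (SAP 2.3 and 2.8, Protocol 9.4.5) does not say how vital status obtained after withdrawal is used.

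**The concern.** Most time-to-event outcomes have to be censored at withdrawal because nothing more is observed. Mortality is the exception: the protocol deliberately keeps its one necessary datum recordable. A rule that censors at withdrawal then discards information the study may hold, and relies on withdrawal being unrelated to the risk of death. A physician's clinical decision to withdraw a subject is a listed reason, so that assumption is not safe.

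What is at stake is the accuracy of a descriptive 12-month safety figure that Protocol 9.4.1 says will be set beside the MitraClip literature. The 30-day MAE and MR measures, the Poisson-type analysis of recurrent hospitalizations and the PMCF success criterion on acute procedural success are not affected.

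**Working it through.** No figure in the plan depends on this rule, so there is none to reproduce. The calculation below only illustrates size.

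**Inputs**
- 1-year mortality 20.3%: TRAMI registry, Protocol Appendix IV.
- N = 1,000: SAP 2.4.
- Assumed, because the documents give no values: share *w* of the cohort withdrawing alive (2, 5 or 10%); time of withdrawal *t* (6 months, or 1 month); hazard ratio HR of death after withdrawal relative to subjects still in the study (0.5, 1, 2, 3); constant hazards.

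**Censoring at withdrawal.** λ = -ln(1 - 0.203) = 0.227 per year. Kaplan-Meier then estimates the in-study hazard only and gives 20.3% in every scenario.

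**True mortality.** With S = exp(-λt):

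truth = 1 - [(S - w)·exp(-λ(1 - t)) + w·exp(-HR·λ(1 - t))]

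Example with w = 10%, t = 0.5, HR = 3: S = 0.893; (0.893 - 0.10) × 0.893 = 0.708; 0.10 × exp(-0.340) = 0.071; truth = 1 - 0.779 = 22.1%, which is 1.8 points above 20.3%.

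Truth minus censored estimate, percentage points, withdrawal at 6 months:

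| Withdrawn | HR 0.5 | HR 1 | HR 2 | HR 3 |
|---|---|---|---|---|
| 2% | -0.1 | 0 | +0.2 | +0.4 |
| 5% | -0.3 | 0 | +0.5 | +0.9 |
| 10% | -0.5 | 0 | +1.0 | +1.8 |

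With 10% withdrawing at 1 month (t = 1/12) the row is -0.9, 0, +1.5, +2.8.

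**Other baselines.** Spreading withdrawal evenly in hazard over the year, and using the other 1-year mortalities in Appendix IV (15.3% Sentinel, 25.8% TVT), the shift over the whole grid runs from -0.7 to +2.2 points.

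**Precision for comparison.** 1.96 × √(0.203 × 0.797 / 1000) = 2.5 points (2.2 at 15.3%, 2.7 at 25.8%).

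**Counting deaths but not survival time.** Suppose a share *c* of deaths after withdrawal is captured and counted, while all other withdrawn subjects are still censored at withdrawal. Subjects whose deaths are counted stay at risk until death; the others leave at *t*. The Kaplan-Meier estimate is 1 - S·exp(-H), where H is the integral over u from 0 to 1 - t of

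[(S - w)λe^(-λu) + c·w·HR·λe^(-HR·λu)] / [(S - w)e^(-λu) + c·w(e^(-HR·λu) - e^(-HR·λ(1-t)))].

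- All deaths captured, withdrawal at 6 months: overstates the truth by 0.2 to 1.1 points across HR 0.5 to 3.
- All deaths captured, withdrawal at 1 month: overstates by up to 1.8 points.
- Half captured, withdrawal at 6 months, HR 3: understates by 0.1, 0.2 and 0.4 points at 2, 5 and 10% withdrawal.

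With all deaths captured and withdrawal at 6 months, this half-measure is worse than censoring at HR 1 or below, about equal at HR 2, and better at HR 3 (errors of 0.2, 0.4 and 1.0 points against 0.4, 0.9 and 1.8). Neither dominates.

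**The case against.** The strongest reply is that the SAP is not silent. A reader might infer from the first censoring sentence, which is limited to subjects without events, that the plan leaves the treatment of later deaths open. The withdrawal sentence does give an answer, however: censor. That stands, so the complaint is that the rule suits mortality poorly, not that it is undefined.

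A reader might also infer that mortality will be understated. The documents do not support that. They give no withdrawal rate, no timing and no prognosis after withdrawal; the bias is zero if withdrawal is non-informative and can go either way.

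The size is modest. Every 6-month scenario is below the 2.5-point half-width, no hypothesis test or sample size rests on 12-month mortality, and all the inputs that generate a bias are assumed. This stands too and limits the weight of the point. It does not remove it, because this bias does not shrink as the sample grows.

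The eCRF fields are not visible. A date may already be collected with vital status, in which case the fix is wording only.

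Finally, a reader might extend the point to 12-month MAE ("MAE is defined as a composite of all-cause Death, Myocardial Infarction, Stroke" and non-elective surgery) or to first heart failure hospitalization. No visible passage assigns Kaplan-Meier to either; SAP 2.2.1.2 and 2.3 also allow simple percentages, and the SAP's events of interest may have been listed in text that was removed. Those extensions are conditional only.

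**Conclusion.** The point holds as a minor improvement to the analysis of all-cause mortality. As written, SAP 2.2.2 discards post-withdrawal deaths and known-alive time that Protocol 5.5 allows to be recorded. At 20.3% mortality, with 2 to 10% withdrawing at 6 months and hazard ratios of 0.5 to 3, the censored estimate is between 0.5 points too high and 1.8 points too low. With 10% withdrawing at 1 month it is between 0.9 too high and 2.8 too low; only the extreme of that range exceeds the 2.5-point half-width. All of this rests on assumed withdrawal shares, timing and hazard ratios, and on constant hazards. The documents do not show that withdrawal will be frequent or informative, so they support neither a claim of material bias nor a claim about its direction.

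**What to change.** Add to SAP 2.2.2:

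- For all-cause mortality, a death recorded after withdrawal counts as an event, and a withdrawn subject not known to have died is censored at the last date known alive.
- The completeness of post-withdrawal status is reported, and censoring at withdrawal is kept as a sensitivity analysis.
- If status is obtained mainly for subjects who died, both analyses are reported with a statement that neither is unbiased. Counting deaths alone generally overstates mortality when all are captured; censoring understates it if withdrawn subjects die faster.
- Non-fatal endpoints stay censored at withdrawal.
- If 12-month MAE is reported as a time-to-event rate, its death component follows the same rule. If first heart failure hospitalization is so reported, use the cumulative incidence function with death as a competing event.

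In Protocol 5.5 or the eCRF instructions, ask for a date with the deceased/alive status, for survivors as well as for subjects who died.

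Cost: a few sentences, plus collecting a status date and tracing survivors where sites do not already do so. Comparability with older reports is slightly reduced; the sensitivity analysis retains the mortality result under censoring at withdrawal.
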